2.3 Study-Plan

This study is a retrospective single centre cohort study in order to investigate the impact of high NaMELD on long term outcomes after liver transplantation. For this purpose, a comprehensive data analysis will be performed.

3. OBJECTIVES

3.1 Primary Objectives

Long-term patient survival of high NaMELD recipients after liver transplantation.

3.2 Secondary Objectives

To assess clinical and laboratory parameters during hospital stay and within and up to 15 years Follow up.

4. Primary and Secondary Endpoints/Outcome Measures

- **Primary Endpoints**
- Patient survival

4.1 Secondary Endpoints

- Biochemical assessment of liver and organ function including laboratory parameters during the Follow up (Day 7, 3 months, 6months, yearly).
- Meaning for health care related parameters including ICU stay.
- Reasons for graft loss, death, and re-transplantation.

4.2 Overall Description of Trial Participants

Adult patients (18 years or older) who received a liver transplantation in participating hospitals (Toronto General Hospital) and satisfy the inclusion and exclusion criteria outlined below are eligible to take part in this study.

4.2.1. Inclusion Criteria

- Patient registered for liver transplantation.
- Patients at least 18 years of age

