1. SYNOPSIS

Study Title	Elucidating major impact factors for high MELD recipient outcomes after orthotopic liver transplantation in adults.
Trial Design	Retrospective cohort study.
Trial Participants	High MELD patients receiving a liver transplant.
Planned Sample Size and Trial Duration	Eligible patients that received a liver graft within the last 15 years.
Trial duration	Up to 15 years Follow up.
Data Collection Period	January 01, 2010 to December 31, 2025
Primary Objective	To identify main risk factors for long term survival of high Sodium medical Model for End-Stage Liver Disease (NaMELD) patients and long-term graft survival after liver transplantation, with the aim prevent and treat pivotal factors prior to transplantation.
Secondary Objectives	
To confirm the risk factors for other long and short-term complication in high NaMELD patients.
 
To investigate the combination of risk factors and NaMELD graduation over time.

Primary Endpoint	Patient survival after liver transplantation.
Secondary Endpoints	
Assessment of biochemical parameters of liver function in the recipient during the initial postoperative phase and during the Follow up.
 
ICU stay.
 
Reasons for graft loss, death and retransplantation.

2. BACKGROUND AND RATIONALE:

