2.2 Aim of the Study

We will create a comprehensive database to address several questions regarding the selection and outcome of liver transplantation in high NaMeld recipients:

1. Is the change of NaMeld score (delta Meld) prior to liver transplantation predictive for post-transplant outcome?
2. What are the characteristics of futile liver transplants in high NaMeld patients (high NaMeld recipients that do well vs early death)
3. Is exceeding the NaMeld threshold of 30 predictive of poor outcome?
4. Do all NaMeld factors are of equal importance for the prediction of futile outcome in high Meld recipients?

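### The Synopsis and primary objective limit the cohort to high-NaMELD recipients, the eligibility text sets no NaMELD limit, and high is never defined, so the comparator for the NaMELD-30 question is not fixed

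*Protocol*

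**What the plan says.** **Text that restricts the cohort.** The Synopsis row on trial participants reads "High MELD patients receiving a liver transplant". The primary objective, in the Synopsis and again in section 3.1, concerns survival of high-NaMELD recipients. Section 2.2 introduces its four aims as questions about high-NaMELD recipients.

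**Text that does not.** Section 4.2 says that adults "who received a liver transplantation in participating hospitals (Toronto General Hospital) and satisfy the inclusion and exclusion criteria outlined below are eligible". The inclusion list in 4.2.1 has two entries: "Patient registered for liver transplantation" and "Patients at least 18 years of age". The exclusions in 4.2.2 cover multi-organ transplants, enrolment in trials of other unlicensed therapy, age under 18, and retransplants. None of these sections contains a MELD or NaMELD criterion.

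**Text that needs a contrast.** Aim 3 in section 2.2 asks "Is exceeding the NaMeld threshold of 30 predictive of poor outcome". Section 2.3 gives the study's purpose as the impact of high NaMELD on long-term outcome. Section 6 makes patient survival in different groups the main outcome measure but does not name the groups.

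**The concern.** A reader who extracts data under the Synopsis and one who extracts under sections 4.2 to 4.2.2 will build different datasets, and nothing in the protocol says which text governs. The difference bears directly on Aim 3. Whether passing a threshold predicts outcome can be estimated only if recipients on both sides of it are in the data.

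The missing definition of high adds to the problem. The number 30 appears once, inside Aim 3, as the threshold under test. The Synopsis speaks of high MELD in one row and high NaMELD in another. Appendix 8.2 lists the components of the score, but no section says which time point would classify a recipient. In a retrospective study the outcomes already exist, so a cut-off left open can be chosen after they have been seen.

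**Working it through.** The protocol states no sample size, event count, effect size or score distribution, so there is no figure to reproduce. The check is to set the texts side by side and ask who could serve as the comparator for Aim 3.

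**Step 1: who is in the cohort?**

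| Source | Transplant received? | NaMELD limit |
|---|---|---|
| Synopsis, trial participants | Yes | High MELD, no number |
| Synopsis, planned sample size ("Eligible patients that received a liver graft within the last 15 years") | Yes | None of its own; refers to eligibility |
| Section 3.1, primary objective | Yes | High NaMELD, no number |
| Sections 4.2, 4.2.1 and 4.2.2 | Yes, through 4.2 | None |

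All four agree that a transplant was received. They disagree on whether the score restricts entry.

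**Step 2: what does Aim 3 need?** The exposed group is NaMELD above 30. The comparator is every cohort member at or below 30.

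**Step 3: what comparator does each reading leave?** Let *c* be the unstated cut-off for high.

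- *Synopsis reading, high means above 30 or a stricter limit.* Every member is above 30. The comparator is empty and the contrast cannot be estimated.
- *Synopsis reading, c below 30 (an assumption).* The comparator is recipients from *c* to 30. A contrast exists, but it sets those above 30 against a band just under 30, not against ordinary recipients.
- *Eligibility reading.* The comparator is all adult first, liver-only recipients at or below 30 who meet the other criteria. Aim 3 can be answered as asked.

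**Step 4: which other aims are affected?** Aims 2 and 4 are posed within high-score recipients, so they need no low-score comparator. They do need a definition of high. The purpose in section 2.3 needs a contrast for the same reason as Aim 3.

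One of the two readings therefore supports all the aims once high is defined. The other cannot answer Aim 3, or answers a narrower question.

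**The case against.** The best defence is that the eligibility section is the operative text and the Synopsis only a summary. On that view lower-score recipients are already in, high-score recipients are simply the group of main interest, and Aim 3 has its comparator. This is a sensible way to read the protocol, and it shows that a usable cohort is already written down. It does not remove the contradiction. The restriction also appears in the primary objective in the body of the protocol, no text gives one section precedence, and high stays undefined on either reading.

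It can also be said that group definitions and the form of the NaMELD term may be left to a statistical analysis plan, which is not at hand. That is fair for the form of the term. It does not cover who is in the cohort: the protocol fixes that and here contradicts itself, and an analysis plan cannot bring back records that were never extracted.

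Three stronger readings are tempting, and the documents do not support them.

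- *Patients who were registered but never transplanted would enter.* A reader might infer this from "Patient registered for liver transplantation" taken alone. Section 4.2 joins receipt of a transplant to the criteria with *and*, and the Synopsis sample-size row also requires a graft. The word registered is loose, but it admits nobody without a transplant.
- *Recipients would carry immortal waiting time.* Nothing starts the clock at registration. The primary endpoint is "Patient survival after liver transplantation", and Appendix 8.2 collects the date of transplant but no registration date.
- *The study loses a calculable share of information by cutting NaMELD at 30.* Any such figure would need the share of recipients above 30, which the protocol does not give. It would measure the cost of dichotomising a score, which is a different matter from a disagreement over eligibility. Nor does the protocol say that NaMELD will be analysed only as above or below 30.

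**Conclusion.** The point holds as a contradiction within the protocol. The Synopsis and the primary objective restrict the cohort by score, the eligibility text does not, and the restricting term has no number, no consistently named score and no time point.

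The size is logical, not numerical. Under the Synopsis, Aim 3 has no comparator if high means above 30, and a truncated one if high starts lower. Under the eligibility text it can be answered. The statement that there is no comparator at all therefore rests on the assumption that high means above 30; 30 is the only threshold in the protocol, but the protocol does not adopt it as the definition. It would be wrong to say that both readings fail, since the eligibility text already gives a workable cohort. The matter should be settled before data are extracted.

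**What to change.** 1. Align the Synopsis and section 3.1 with sections 4.2 to 4.2.2, so that the cohort is all adults who received a first, liver-only transplant in the data window, at any NaMELD, subject to the existing exclusions. High-NaMELD recipients can remain the group of main interest within it.
2. Reword the first inclusion entry in 4.2.1 so that it refers to receipt of a transplant, as 4.2 does. This is a wording change only.
3. Define high NaMELD in advance by a number, for one named score at one named time point. Above 30 at transplant is one option, since 30 is the only threshold the protocol offers.
4. Name recipients at or below 30 as the reference group for Aim 3 and answer it in the whole cohort, preferably also with NaMELD as a continuous term. Run Aims 2 and 4 within the high stratum.

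The cost is a short amendment. If only high-score records had been planned, lower-score records must also be drawn from the same hospital database, which is modest extra work. If extraction was already to follow sections 4.2 to 4.2.2, there is no extra data cost.

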2.1 Liver Transplantation and Model for End-Stage Liver Disease

Liver transplantation (LT) represents an important curative option for end stage liver disease such as decompensated cirrhosis, which remains a major challenge for today's health care system. The Model for End-Stage Liver Disease (MELD) is a worldwide-established scoring system for the evaluation of the severity of liver disease in allocation processes. However, the interpretation of MELD in clinical practice, particularly with regard to prioritizing potential liver transplant recipients, has revealed some hazards. These include the adaptation of MELD based on patient's characteristics, e.g. the presence of hepatocellular carcinoma, kidney failure and cardiovascular disease (Freeman et al. 2002). In addition, the remaining paucity of organ donors contributes to a rising number of transplantations of high MELD recipients. This leads to the risk of impaired outcomes, especially considering the interaction of additional donor and recipient risk factors, such as extended cold preservation, kidney function and warm ischemia (Schlegel et al. 2017). For a certain patient cohort living donation might represent a feasible approach as reported previously for high MELD patients (Selzner et al. 2010). Overall, the interaction of donor and recipient characteristics on the outcomes after LT in high MELD patients remains a scarcely investigated field. Therefore, the identification of factors influencing patient's outcomes after orthotopic liver transplantation becomes increasingly important, especially in high MELD recipients.

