4.2.2. Exclusion Criteria

- Patients undergo transplantation of organ(s) in addition to the liver.
- Patients who are enrolled in clinical trials of other unlicensed therapy.
- Patients younger than 18 years
- Patients for retransplant

5. Data Collection Procedure:

Data from January 01, 2010 to December 31, 2025 will be collected from hospital specific database. The collected data will be identified by unique study identifier only. Data will be stored for ten years after study completion in accordance with requirements of the corresponding ethic committees; publication or data source file stored will not contain any personal identifiers.

6. Data Analyses:

All statistical data will be generated by using JMP 13 (SAS Institute, Cary, NC), SPSS 22 statistical package (IBM, Chicago, IL, USA), or R (The R Foundation for Statistical Computing, Vienna, Austria). The main outcome measure will be the incidence of patient survival among different groups. Cumulative overall rejection-free rates will be calculated by Kaplan-Meier methods and differences between curves will be evaluated with the log-rank test and Bonferroni or Holm's correction. Continuous variable data will be analyzed nonparametrically using the Wilcoxon / Kruskal-Wallis' correction.

Categorical variables will be summarized as counts and proportions and compared by Chi squared test or Fisher's exact test as appropriate. These results will be represented as Odd's ratio or Hazard ratio with 95% confidence interval (CI). $P < 0.05$ will be considered statistically significant.

7. Ethical Consideration:

This protocol was approved by the local ethic committees of participating centers. No study activities will begin until approval is obtained. A waiver of informed consent is requested for this study since it meets the requirements for the common rule. Namely, it would be impractical to attempt to obtain consent for this study since many of these patients may now be deceased and/or lost to follow-up. Further, the exclusion of any patients would impact the quality of the study data. Finally, the study involves minimal risk to participants, as no change to patient care is taking place.

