8.2 Recipient Variables

Recipient Variables		
Overall Characteristics	Date of transplant	
	Date of Death	
Biographic Characteristics	Date of Retransplant	
	Date of last clinical visit	
	Age at Transplant	
	Height	
	Weight	
	Gender	
	Etiology of liver Disease	
	Bilirubin; INR; Creatinine; Sodium at MELD	
	Timepoints	
	Creatinine	D1-7
		3 months
		D90
		6months
		yearly
	eGFR	D1-D7
		3 months
		6 months
		yearly
		D90
	INR	6months
		12months
		D7
		3 months
		D90
	AST	6months
		Yearly
		D1 – D7
		3 months
		6months
	ALT	yearly
		D1 – D7
		3 months
		6months
		yearly

	Bilirubin	D7
		3 months
		6months
		yearly
	Sodium	D7
		3 months
		6months
		Yearly
	Alkaline	D7
	phosphatase	3 months
		6months
		Yearly
	Graft Survival at 1, 3, 5, 10 yrs	
Patient Survival at 1, 3, 5, 10 yrs		
Post-transplant ICU Stay		
Readmission within 30 days (1=yes; 0=no)		
Retransplantation date		
Cause of Graft Loss		
Cause of Death		

Freeman, Richard B.; Wiesner, Russell H.; Harper, Ann; McDiarmid, Sue V.; Lake, Jack; Edwards, Erick et al. (2002): The new liver allocation system: moving toward evidence-based transplantation policy. In: Liver Transplantation 8 (9), S. 851–858. DOI: 10.1053/jlts.2002.35927.

Selzner, Markus; Kashfi, Arash; Cattral, Mark S.; Selzner, Nazia; McGilvray, Ian D.; Greig, Paul D. et al. (2010): Live donor liver transplantation in high MELD score recipients. In: Annals of surgery 251 (1), S. 153–157. DOI: 10.1097/SLA.0b013e3181bc9c6a.

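### Eligibility admits any cause of liver disease and the named tests are not stratified by cause, so the crude delta MELD and NaMELD >30 associations can partly reflect acute versus chronic disease

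*Protocol*

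**What the plan says.** Protocol section 4.2.1 has two inclusion criteria: "Patient registered for liver transplantation" and "Patients at least 18 years of age". Section 4.2.2 has four exclusions: "Patients undergo transplantation of organ(s) in addition to the liver", "Patients who are enrolled in clinical trials of other unlicensed therapy", age under 18, and "Patients for retransplant". No criterion names a cause of liver disease, and acute liver failure is mentioned nowhere in the protocol.

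The rationale in section 2.1 introduces transplantation for "end stage liver disease such as decompensated cirrhosis". Section 2.2 then asks, among other things, whether the pre-transplant change in NaMELD predicts outcome (question 1) and whether a NaMELD above 30 predicts poor outcome (question 3).

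Section 6 names Kaplan-Meier curves with log-rank tests, Wilcoxon/Kruskal-Wallis tests, and chi-squared or Fisher tests. It states no stratification or adjustment. Section 8.2 lists "Etiology of liver Disease" among the recipient variables, but section 6 gives it no role.

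**The concern.** Delta MELD and the threshold of 30 are to be read as prognostic markers, which presumes that a given score, or a given change in it, means much the same across the cohort. That presumption is doubtful for acute liver failure. Such a patient may have no earlier score from a stable phase, so that delta MELD is undefined, or may show an extreme rise over a few days. Disease type is then tied to the exposure. If early mortality also differs by disease type, a crude comparison of rapid with slow risers, or of recipients above and below 30, mixes the effect of the score with the effect of the disease.

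What is at stake is the use of the result. The primary objective in the synopsis is to find risk factors that can be prevented or treated before transplantation. A rapid rise that only marks a different disease would not serve that purpose. A larger cohort does not remove the distortion; it makes a spurious result more likely to be significant.

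**Working it through.** The protocol states no sample size, event count, mortality or delta MELD cut-off, so there is no figure of its own to reproduce. The check has two parts.

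**1. Reading.** Sections 4.2.1 and 4.2.2 leave acute liver failure eligible, the tests in section 6 carry no strata, and etiology is collected in 8.2. Followed as written, the plan makes crude comparisons across all causes.

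**2. Illustration.** All inputs below are assumptions. The exposure is a rapid rise in NaMELD, and it has no effect on death within either disease.

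Notation: *a* = acute share of the cohort; *dA*, *dC* = early death risk in acute and chronic disease; *rA*, *rC* = proportion of each that rises rapidly.

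- Proportion rising rapidly: P = a·rA + (1−a)·rC
- Risk in rapid risers: D1 = [a·rA·dA + (1−a)·rC·dC] / P
- Risk in the others: D0 = [a·(1−rA)·dA + (1−a)·(1−rC)·dC] / (1−P)
- Crude odds ratio: [D1/(1−D1)] / [D0/(1−D0)]

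The chance of P<0.05 comes from the normal-approximation two-sided test of two proportions.

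*Partial overlap* (rA = 0.90, rC = 0.20, a = 0.10). P = 0.09 + 0.18 = 0.27, so acute cases are 0.09/0.27 = 33% of rapid risers.

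- dA 30%, dC 10%: D1 = (0.027 + 0.018)/0.27 = 16.7%; D0 = (0.003 + 0.072)/0.73 = 10.3%; odds ratio 1.75. Chance of P<0.05: 34%, 57% and 77% at N = 300, 600 and 1000.
- dA 20%, dC 10%: D1 = (0.018 + 0.018)/0.27 = 13.3%; D0 = (0.002 + 0.072)/0.73 = 10.1%; odds ratio 1.36. Chance at N = 1000: 31%.
- dA = dC = 15%: odds ratio 1.00.
- dA 10%, dC 15%: D1 = (0.009 + 0.027)/0.27 = 13.3%; D0 = (0.001 + 0.108)/0.73 = 14.9%; odds ratio 0.88.

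With a from 5% to 20% and rC of 20% or 30%, the odds ratio runs from 1.10 to 2.19 when acute mortality is higher (20% or 30% against 10%, or 25% against 15%). It runs from 0.81 to 0.95 when acute mortality is lower (10% against 15%).

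*Complete concentration* (all acute cases in the top quarter of delta MELD, dC = 10%). The top-quarter risk is [a·dA + (0.25−a)·0.10]/0.25, against 10% in the rest.

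| a | dA | Top-quarter risk | Odds ratio | Chance of P<0.05, N = 1000 |
|---|---|---|---|---|
| 5% | 20% | (0.010+0.020)/0.25 = 12% | 1.23 | 16% |
| 10% | 20% | (0.020+0.015)/0.25 = 14% | 1.47 | 42% |
| 15% | 30% | (0.045+0.010)/0.25 = 22% | 2.54 | 99% |

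This second model is an upper case. It puts every acute patient in the top quarter, although those without an earlier score would have no delta MELD at all. At a = 10% and 20% against 10% mortality, moving to partial overlap lowers the odds ratio from 1.47 to 1.36 and the chance of significance from 42% to 31%.

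In both models, restricting to chronic disease or stratifying by disease type returns an odds ratio of 1.00, because that is the assumed truth within each disease. Only a rapid-rise split was computed. The same formulas would apply to NaMELD >30 with the proportions above 30 in place of *rA* and *rC*, but no inputs for that are at hand.

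**The case against.** The strongest reply is that section 6 does not say that causes will be pooled. It compares groups that it does not define. Stratification and adjustment are ordinary content of a statistical analysis plan, which is not at hand, and the variable they need is collected. This stands in part: a later plan could settle the analysis. But who enters the cohort is a protocol decision, and sections 4.2.1 and 4.2.2 make it. Adjustment also cannot create a delta MELD for a patient with no meaningful earlier score.

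A second reply is that questions 1 and 3 ask only whether the score is predictive. An association that comes from disease mix still predicts in the cohort studied. That is fair for pure prediction, but not for the stated aim of preventing and treating risk factors before transplantation.

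A third reply is that no input comes from the protocol. That stands in full: the acute share, mortality and degree of overlap are unknown, and the bias may be positive, negative or nil.

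Two stronger readings are tempting. A reader might infer from "curative option for end stage liver disease such as decompensated cirrhosis" that the study is meant for decompensated cirrhosis and that eligibility contradicts it. The wording gives an example and not a target population, and broad entry fits an aim about high-MELD recipients in general. A reader might also infer that the answers to all four questions in section 2.2 are invalid. Nothing was computed for questions 2 to 4, and the mechanism is argued only for questions 1 and 3.

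**Conclusion.** The point holds as a confounding risk for questions 1 and 3. Acute liver failure is eligible, the stated tests do not separate it, and the crude associations of delta MELD and NaMELD >30 with outcome can partly reflect disease type. This needs two conditions: acute and chronic recipients must differ in their NaMELD course or level, and they must differ in mortality. The first is clinically plausible but is not documented in the protocol; the second is unknown.

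The illustrative odds ratios of about 0.8 to 2.5 show what is possible for a rapid-rise split under assumed inputs; they do not estimate the bias in this cohort. The top of the range needs a 15% acute share, threefold mortality and complete concentration all at once. The documents do not support saying that an observed association would arise wholly from disease mix, or that the bias must exaggerate risk. The change is worth making because it is cheap and removes an ambiguity that the results alone could not resolve.

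**What to change.** Add a sentence to section 6, with a matching note at "Etiology of liver Disease" in section 8.2:

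- Code etiology so that acute liver failure is separable from chronic liver disease. The field is listed without coding, and a recorded cause need not show which of the two applies.
- Leave acute liver failure out of the delta MELD analysis (question 1).
- For NaMELD >30 (question 3) and the survival risk-factor analyses, either stratify the tests and models by acute versus chronic disease, or run them in chronic disease and report acute cases separately.
- Report the number of acute cases and their mortality, so that readers can judge how much the separation matters.

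Eligibility need not change; the all-causes cohort can stay. The cost is a delta MELD cohort smaller by the acute share (5% to 20% under the assumptions above, for example 900 instead of 1000 at 10%) and possibly some recoding of etiology from the records.
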